However, it should be noted that a recent report described evidence of rapid progression of disease after treatment with an anti-PD-1 antibody in patients with adult T-cell leukemia-lymphoma (ATLL), which is a subtype of PTCL. All 3 patients with ATLL treated on a phase 2 clinical trial of nivolumab experienced rapid clinical progression of disease with leukocytosis, hypercalcemia, renal dysfunction, and elevated lactate dehydrogenase levels. Concurrently, HTLV-1 proviral loads were noted to be increased in 2 patients and 2 patients also developed circulating atypical lymphocytes and hyperbilirubinemia.⁵¹ In a separate study, using a mouse model of human T-cell lymphoma, it was demonstrated that PD-1 can function as a tumor suppressor.⁵² Although, thus far, this phenomenon of rapid progression after anti-PD-1 therapy has only been described in ATLL, it is theoretically possible in other PTCL subtypes.

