5.7 Replacement of Subjects

During the Phase 1 portion of the study, subjects will be replaced for any of the following:

- Missed any doses of pralatrexate during the DLT period (not due to DLT).
- Did not receive the doses of pembrolizumab during the DLT period (not due to DLT).

Subjects who are replaced for missed doses may continue to receive study treatment if there is clear clinical benefit, but will not be included in DLT analysis.

During the Phase 2 portion of the study, subjects who did not receive at least 1 dose of pembrolizumab and 1 dose of pralatrexate, or who did not have a tumor response assessment (except due to progression of disease prior to the first tumor response assessment) will be replaced. If a patient discontinues study treatment prior to the first response assessment due to progressive disease, the treating physician is encouraged to obtain imaging to confirm progression.

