- Safety visit to occur 30 (-2/+7) days post-last dose of protocol therapy. At the end of the treatment, each subject will be followed for 30 days for adverse event monitoring, and 90 days for severe adverse events and events of clinical interest. Safety follow up may be extended until resolution/stabilization of reportable AEs.
- Protocol therapy will continue for a maximum of 24 months until progressive disease, unacceptable toxicity, withdrawal of consent, pregnancy of the subject, non-compliance, or administrative reasons.
- Leucovorin will be administered orally three times daily (every 8 hours) for 2 days for a total of 6 doses **beginning 24h (+/- 2h) after each dose of pralatrexate** is administered. Refer to [Section 5.13.2](#).
- Vitamin B12 (1 mg IM) will be administered anytime within 10 weeks prior to initiation of pralatrexate (per pralatrexate product insert) and can be administered during screening, and will be administered every 3 cycles. Administration should continue during the full course of pralatrexate therapy and for 30 days after the last dose of pralatrexate. Refer to [Section 5.13.2](#).
- Vital signs: Weight, heart rate, blood pressure, respiration rate, and temperature. Height required only at baseline.
- To be done between D15 and D21 (-3 days).

- h. Disease staging is performed at screening and every 4 cycles until disease progression or off study therapy. Disease staging will be by either PET/CT (preferred) or CT scan, but, in patients with FDG-avid disease, it will be preferred (but not mandatory) to have PET/CT at baseline, Cycle 4 and every 8 cycles thereafter. Note: if there is no evidence of neck involvement by lymphoma at baseline, CT of chest, abdomen and pelvis (C/A/P) can be performed instead of N/C/A/P at subsequent re-staging.
- i. Tumor biopsy tissue will be obtained after routine diagnostic biopsy is done with the patient's consent. Exception can be granted by the PI if a biopsy is not feasible and/or safe. For the EOT time point, tumor tissue will be collected from a standard of care tumor biopsy performed at the time of lymphoma relapse/progression (if such a biopsy is performed), unless the tumor is inaccessible or there is a safety concern.
- j. Following initial screening, and unless clinically indicated, bone marrow specimens will be collected only to confirm CR.

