- k. Female subjects of childbearing potential should have a negative urine or serum pregnancy within 72 hours prior to receiving the first dose of study medication.
- l. Do not repeat this time point for correlative blood collection: peripheral blood is collected prior to study treatment/procedures on C1D1, C2D1, C4D1, C5D1, and at EOT (see also footnote t).
- m. Day 8 labs/visits are set up because of pralatrexate administration on these days. If a patient discontinues pralatrexate (and continues with pembrolizumab alone), these Day 8 labs/visits can be omitted.
- n. Folic acid supplementation is to begin within 10 days (as early as possible) prior to the first dose of pralatrexate administration (per pralatrexate product insert). However, if folic acid was not taken but MMA (methylmalonic acid) and HCY (homocysteine) levels were checked and are in normal range at screening, the investigator can decide to start study therapy immediately. Administration should continue during the full course of pralatrexate therapy and for 30 days after the last dose of pralatrexate. Refer to [Section 5.13.2](#).
- o. If the urine test is positive or cannot be confirmed as negative, a serum pregnancy test will be required. Pregnancy testing will also be performed whenever an expected menstrual cycle is missed or when pregnancy is otherwise suspected.
- p. Assessments to be performed within 10 days of treatment discontinuation (except tumor imaging, see footnote r). Assessments performed after last dose of study agent and within 7 days of the decision to end treatment may serve as EOT assessments.
- q. For participants yet to progress. Follow-up will occur every 12 weeks (-/+ 7 days) starting from last on-treatment scan. After one year, the imaging time point will occur every 18 weeks (+/- 7 days). Response Follow-up will be performed until progression or off study, and for at least one year in each patient who did not progress yet.
- r. PET-CT (or CT) at time of discontinuation (EOT) will only be performed in patients who discontinue treatment for disease progression. Note: if a previous scan was obtained within 4 weeks prior to the date of discontinuation, then repeating the scan at treatment discontinuation is not mandatory. For patients who discontinue treatment for other reasons than disease progression (e.g. for toxicity, CR): PET-CT (or CT) will not be performed at EOT and will be performed 12 weeks

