11.0 ENDPOINT EVALUATION CRITERIA/MEASUREMENT OF EFFECT

11.1 Response/Progression

Disease response/progression will be evaluated using 2014 Lugano Classification (see [Appendix B](#))^{8,11}. Participants who meet the definition of progressive disease per Lugano Classification should be evaluated using the LYRIC criteria¹⁰ (see [Appendix C](#)). The ORR and CR rate will also be estimated according to the International Harmonization Project response criteria (Cheson 2007).⁹

PET-CT or diagnostic quality CT of the neck, chest, abdomen, and pelvis (N/C/A/P) with IV contrast will be performed at baseline (within the screening window, 28 days) prior to initiation of study therapy, and then after initiation of study therapy during cycle 4 and every 4 cycles thereafter until disease progression or off study therapy. Refer to [study calendar \(footnote r\)](#) for disease staging at EOT. Disease staging will be by either PET/CT (preferred) or CT scan, but, in patients with FDG-avid disease, it will be preferred (but not mandatory) to have PET/CT at baseline, Cycle 4 and at least every 8 cycles thereafter. In patients with FDG-avid disease, CR must be confirmed with PET/CT. Patients who enter CR with study therapy can be monitored with diagnostic quality CT scans thereafter until disease progression. MRI may be performed at the investigator's discretion for lesions not well-visualized by CT, or if CT with intravenous contrast is contraindicated. PET-CT and CT results will be read by radiology at each study site and investigator response based on radiology reading will be performed. Lymphoma response assessment based on PET-CT/CT will be based on the 2014 Lugano Classification ([Appendix B](#)).^{8,11}

Note: if there is no evidence of neck involvement by lymphoma at baseline, CT of chest, abdomen and pelvis (C/A/P) can be performed instead of N/C/A/P at subsequent re-staging.

Following initial screening, and unless clinically indicated, bone marrow specimens will be collected only to confirm CR.

For patients with progression of disease on imaging, it is strongly recommended that a confirmatory biopsy (performed as standard of care) be obtained whenever possible. Note that only an FDG-negative PET scan will be considered complete remission in patients whose tumor was FDG-avid at baseline.

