12.3.3 Analysis of Anti-tumor Activity

This study will aim to obtain an estimate of the anti-tumor activity of the study combination. ORR will be calculated as the proportion of evaluable patients that have confirmed CR or PR, as defined according to the 2014 Lugano Classification, exact 95% confidence intervals will be calculated for these estimates. Response rates will also be evaluated based on number and type of prior therapy(ies). Duration of response, as well as progression-free survival and overall survival will be estimated using the product-limit method of Kaplan and Meier. As secondary endpoints, the ORR and CR rate will also be estimated according to the International Harmonization Project response criteria (Cheson 2007).⁹

Any patient treated at the RP2D, including those from the Phase 1 portion, will be included in efficacy analyses. Patients will be evaluable for efficacy assessment if they received at least one dose of pralatrexate and at least one dose of pembrolizumab and underwent at least one response assessment. As discussed in [Section 5.7](#), patients will be evaluable for efficacy if they discontinued study therapy prior to the first response assessment because of progression of disease rather than solely because of unacceptable toxicity, withdrawal of consent, or investigator's decision.

12.3.4 Safety Analysis and Stopping Rules for Excessive Toxicity or for Rapid Disease Progression

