Because of the unique immune-related adverse events (IrAEs) observed with checkpoint inhibitors, we will monitor for "unacceptable toxicity" (defined in [Section 11.2](#)) and treatment-related mortality at any time during study treatment with this new combination of drugs. This monitoring will include all patients treated on the study regardless of the dose levels they were on. The expected rate of "unacceptable toxicity" should not be >33%. If the rate of "unacceptable toxicity" is >33% after at least 6 patients are treated on study at any bi-annual safety review, or if a 2nd death that is at least possibly related to study treatment occurs regardless of the number of patients on study, accrual will be halted and a full review of these events will be performed by the City of Hope Data Safety Monitoring Committee (DSMC). Patient accrual will not resume until approved by the DSMC to do so. These rules are in addition to the bi-annual review of all toxicities submitted to the City of Hope Data Safety Monitoring Committee (DSMC). Patients with ongoing toxicity will be followed until resolution or stability.

In addition, because of the evidence that PD-1 may act as a tumor suppressor in preclinical T-cell lymphoma models and the recent reports of rapid disease progression in patients with ATLL, a subtype of PTCL, we will also monitor for rapid progression of disease. If at any bi-annual safety review during the conduct of the study, and after at least 3 patients are treated on study, > 33% of patients who received at least one dose each of pembrolizumab and pralatrexate (regardless of the dose level or if during the phase 1 or phase 2 portion of the study) experience rapid progression (i.e. an acceleration of disease activity with disease progression according to the 2014 Lugano classification prior to completion of 3 cycles of study therapy), the study accrual will be halted and a full review of these events will be performed by the City of Hope Data Safety Monitoring Committee (DSMC). Patient accrual will not resume until approved by the DSMC to do so.

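### The rapid-progression halt rule counts only Lugano-documented progression, in a window with no scheduled restaging, so undocumented early progression and lymphoma death pull the monitored rate down

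*Combined protocol and SAP*

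**What the plan says.** Section 12.3.4 applies the rule at each bi-annual review once 3 patients are treated. The denominator is everyone who received at least one dose of each drug, and the limit is more than 33%. An event is "an acceleration of disease activity with disease progression according to the 2014 Lugano classification prior to completion of 3 cycles of study therapy". The synopsis repeats the rule without a definition. Neither place names death or clinical progression, and *acceleration* has no criterion.

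Section 11.1 sets imaging at screening, "then after initiation of study therapy during cycle 4 and every 4 cycles thereafter until disease progression or off study therapy". Study calendar footnote g places the cycle 4 scan between days 15 and 21, less 3 days.

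Footnote r provides a scan at discontinuation for patients who stop for progression, but "if a previous scan was obtained within 4 weeks prior to the date of discontinuation, then repeating the scan at treatment discontinuation is not mandatory". It does not say that the previous scan must be an on-treatment scan. The baseline scan "will be performed at baseline (within the screening window, 28 days) prior to initiation of study therapy". For a patient who stops for progression before the first assessment, Section 5.7 says only that "the treating physician is encouraged to obtain imaging to confirm progression". Section 12.3.3 nevertheless keeps that patient for efficacy: "patients will be evaluable for efficacy if they discontinued study therapy prior to the first response assessment because of progression of disease".

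A separate trigger in Section 12.3.4 halts accrual at a second death judged at least possibly related to treatment.

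**The concern.** The rule was added because of reports of rapid progression after PD-1 blockade. Section 2.2 describes patients who "experienced rapid clinical progression of disease with leukocytosis, hypercalcemia, renal dysfunction, and elevated lactate dehydrogenase levels". None of these laboratory features is a Lugano criterion in Appendix B. A patient who deteriorates quickly, and stops or dies before anyone documents Lugano progression, adds 1 to the denominator and 0 to the numerator. The error therefore runs in the unsafe direction: the observed rate is too low and DSMC review comes later than intended.

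**Working it through.** **No stated figure to reproduce.** The plan gives no operating characteristics for this rule.

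**1. Window against schedule.** Three cycles of 21 days end at day 63. Cycle 4 days 15 to 21 fall on days 63 + 15 = 78 to 63 + 21 = 84, or day 75 at the earliest with the 3-day allowance. The first planned restaging is therefore 12 to 21 days after the window closes. If every cycle is shortened to 18 days, the window ends at day 54 and the earliest scan is 54 + 15 − 3 = day 66, so the order does not change.

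**2. What can still supply an event.** There are three routes: an unscheduled scan; a Lugano finding that needs no planned scan (Appendix B includes cutaneous and palpable lesions, and also spleen, marrow and nonmeasured disease such as effusions); or the footnote r scan. A patient who stops in cycles 1 to 3 never completes 3 cycles, so a discontinuation scan can count even if it is read later.

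**3. Reach of the waiver.** With a baseline scan *s* days before C1D1 and a stop on day *d*, the scan is not mandatory if *s* + *d* ≤ 28. If events are uniform over 63 days, the waived share is (28 − *s*)/63. The second share uses a constant hazard from the 3.5-month median PFS cited in Section 2.1.1 (3.5 × 30.4375 = 106.5 days): [1 − 0.5^((28 − *s*)/106.5)] / [1 − 0.5^(63/106.5)].

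| *s* (days) | Last day waived | Share, uniform | Share, constant hazard |
|---|---|---|---|
| 7 | 21 | 33% | 38% |
| 14 | 14 | 22% | 26% |
| 21 | 7 | 11% | 13% |

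Over the full 28-day screening window the uniform share runs from 44% (*s* = 0) to 0% (*s* = 28).

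**4. Effect on the rule.** Simulation assumptions: 36 patients entering uniformly over 48 months, a review every 6 months (my reading of bi-annual), at least 3 treated, all treated patients in the denominator, a halt when the count exceeds 0.33*n*, a true rate of 50%, and uniform event times. Probability of a halt by month 12:

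| Waived patients documented anyway | *s* = 7 | *s* = 14 | *s* = 21 |
|---|---|---|---|
| All | 0.85 | 0.85 | 0.85 |
| 80% | 0.80 | 0.82 | 0.83 |
| 50% | 0.71 | 0.76 | 0.80 |
| None | 0.53 | 0.65 | 0.76 |

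Repeat runs differ by about 0.01. The probability of ever halting is 0.995 with full documentation, about 0.99 at 80%, and 0.78, 0.91 and 0.98 in the bottom row.

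**5. Background if more events are counted.** A constant hazard gives 1 − 0.5^(63/106.5) = 33.6% with a PFS event by day 63. Weibull shapes 1.5 and 2 with the same median give 27.0% and 21.5%. If half of the 33.6% met an acceleration criterion, the rate would be 16.8%. The probability of ever halting, in the same model with full documentation:

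| Qualifying rate | 16.8% | 21.5% | 27% | 33.6% |
|---|---|---|---|---|
| Ever halts | 0.24 | 0.37 | 0.57 | 0.80 |

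Even at a single look, a 33.6% rate crosses the limit with probability 0.62 at *n* = 12 (4 events) and 0.58 at *n* = 30 (10 events).

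**The case against.** The strongest reply is that early progressors will mostly be documented. Section 5.7 encourages imaging for exactly these patients, the study calendar allows extra procedures when clinically indicated, and examination and chemistry (including LDH, calcium and creatinine) are scheduled on days 1 and 8. Footnote r speaks of repeating a scan, which may well mean one that already showed progression. This stands as a limit on size: at 80% documentation the month-12 loss is 0.02 to 0.05. It does not remove the dependence of a halt rule on optional imaging.

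A reader might infer that the baseline scan can excuse imaging throughout cycles 1 to 3. It cannot. From day 29 to day 63, a patient who stops for progression gets the footnote r scan unless another scan was done in the previous 4 weeks.

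A reader might also take the presentation in Section 2.2 as the expected missed case. Those patients had ATLL, which is excluded. Section 2.2 says the phenomenon has been described only in ATLL, though it is theoretically possible in other subtypes. It shows how such progression can look, no more.

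The death trigger is a real backstop. *Possible* attribution in Section 7.1 allows that the disease may be the cause, and the second such death halts accrual without waiting for a review. SAEs are reported whatever their cause. But a lymphoma death judged unrelated or unlikely related triggers nothing, and SAE reports do not enter this count.

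Finally, keeping a patient for efficacy does not by itself contradict the safety rule. The patient is in the safety denominator too, and Sections 5.7 and 12.3.3 do not mention lymphoma deaths. Those sections show only that the protocol already recognises progression before a formal assessment.

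**Conclusion.** The point holds as a gap in the event definition. Undocumented early progression and lymphoma death dilute the monitored rate, and the backstops are partial. The documents do not support the reading that the rule can record no events or would fail to stop a harmful regimen. At a 50% true rate it halts eventually with probability of at least 0.78 in the cases examined, and usually far higher, so the main effect is delay.

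Confidence is high on the text and lower on the size. Baseline-scan timing, the share documented by other routes, event-time shape, accrual pattern and six-monthly reviews are assumptions. The 0.53 to 0.76 range is the extreme for the waiver route, with no waived patient documented by any means; deaths before a scan would add to the loss. The background rates come from a single-agent cohort with a median of 3 prior therapies, so this trial's background may be lower. This is a cheap improvement rather than a flaw that undermines the design.

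**What to change.** 1. In Section 12.3.4 and the synopsis, count as an event Lugano progression, investigator-documented clinical progression, or death from lymphoma before 3 cycles are completed, in each case meeting a written *acceleration* criterion set by the investigators. Do not adopt the broader count without that criterion: the limit would then sit at the roughly 34% background, with a halt probability of about 0.80.
2. Reconcile footnote r with Section 5.7: state whether the baseline scan can be the previous scan, and whether imaging at early progression is required or encouraged. Which applies is for the investigators to decide.
3. State the limit as counts. Read literally, more than 33% means 1 of 3, 2 of 4–6, 3 of 7–9, 4 of 10–12, 8 of 22–24 and 12 of 34–36. Report halt probabilities over plausible background rates, as in step 5 of the working, so that the limit can be confirmed against the broadened definition.

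The cost is protocol wording and one short table. Items 1 and 3 add no scans; whether item 2 does depends on how it is resolved. The downside is more accrual pauses for DSMC review. If the waiver now hides 22% of events (*s* uniform over 0 to 28 days, mean share 14/63), counting them raises the probability of ever halting from 0.14 to 0.24 at a 16.8% qualifying rate, and from 0.53 to 0.80 at 33.6%. Clinical progression is also more subjective than Lugano progression, which is a further reason to write the criterion first.

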13.0 DATA HANDLING, DATA MANAGEMENT, RECORD KEEPING

13.1 Source Documents

Source documents are original documents, data, and records (e.g., medical records, pharmacy dispensing records, recorded data from automated instruments, laboratory data) that are relevant to the clinical trial. The investigator or their designee will prepare and maintain adequate and accurate source documents. These documents are designed to record all observations and other pertinent data for each patient enrolled in this clinical trial. Source documents must be adequate to reconstruct all data transcribed onto the case report forms.

13.2 Data Capture Methods and Management

Data for this trial will be collected using City of Hope's electronic capture system (EDC) that is compliant with 21 CFR Part 11.

Study personnel will enter data from source documents corresponding to a subject's visit into the protocol-specific electronic Case Report Form (eCRF).

13.3 Case Report Forms/Data Submission Schedule

The investigator is responsible for all information collected on participants enrolled in this study. All data collected during the course of this study must be reviewed and verified for completeness and accuracy by the investigator. All case report forms must be completed by designated study personnel. The completed case report forms must be reviewed, signed and dated by the Investigator or designee in a timely fashion.

All data will be collected using electronic data collection, stored as indicated in Section 13.2, and will be submitted according to the timelines indicated in Table 13.3.

Table 13.3 Data Submission Schedule

Form	Submission Timeline
Eligibility Checklist	Complete prior to registration
On Study Forms	Within 14 calendar days of registration
Baseline Assessment Forms	Within 14 calendar days of registration
Treatment Forms	Within 14 calendar days of treatment administration
Adverse Event Report Forms	Phase 1 / Safety Lead-in: Within 7 calendar days of the assessment/notification Phase 2: Within 10 calendar days of the assessment/notification
Response Assessment Forms	Within 10 calendar days of the response assessment
Other Assessment Forms	Within 10 calendar days of the assessment
Off Treatment/Off Study Forms	Within 10 calendar days of completing treatment or being taken off study for any reason
Follow up/ Survival Forms	Within 14 calendar days of the protocol defined follow up visit date or call

